##### *Sensitivity analysis*

Four sensitivity analyses will be performed. In the first, the analysis described above will be performed on the PPS. In the second, performed on the ITT Set without any imputation, any subject who has no assessment of standing alone at Month 15 will be considered as a non-responder; otherwise the analytical method is the same as that for the main analysis.

In the third sensitivity analysis, performed on the ITT Set, any subject who is missing the Month 15 assessment due to treatment failure or death will be considered to be a non-responder. Any subject who is missing the Month 15 assessment for any other reason will be excluded from the analysis; otherwise the analytical method will be the same as that for the main analysis. In the fourth sensitivity analysis, only the subset of subjects in the ITT Set who have non-missing values for standing alone at 15 months will be analyzed.

### 5.6.5.2 Summary of analyses

#### Summary of analyses for the secondary endpoint, Proportion of subjects who achieve standing alone at 15 months

Analysis Method	Final Analysis - Population: further notes
Main analysis	
Logistic regression adjusting for each subject's age at screening and baseline ability to stand alone. Subjects who terminate the study prior to the 15-month assessment due to treatment failure or death will be considered as a non-responders	ITT, impute missing 15-month values per Section 5.6.2
Sensitivity analyses	
Logistic regression adjusting for each subject's age at screening and baseline ability to stand alone. Subjects who terminate the study prior to the 15-month assessment due to treatment failure or death will be considered as a non-responders	PPS, impute missing 15-month values per Section 5.6.2
Logistic regression adjusting for each subject's age at screening and baseline ability to stand alone. Subjects who terminate the study prior to the 15-month assessment due to treatment failure or death will be considered as a non-responders	ITT
Logistic regression adjusting for each subject's age at screening and baseline ability to stand alone. Subjects who terminate the study prior to the 15-month assessment due to treatment failure or death will be considered as a non-responders	ITT: completed/ discontinued subjects with missing Month 15 not deemed due to treatment failure or death are excluded
Logistic regression adjusting for each subject's age at screening and baseline ability to stand alone	ITT, with non-missing 15-month values

### 5.6.6 Proportion of subjects who achieve walking with assistance at 15 months

This will be analyzed using the same main and sensitivity methods as described in Section 5.6.5.

### **5.6.7 Interim Analysis**

No testing of the secondary endpoints will be performed at the interim but summary statistics for each measure may be provided as follows. For the HFMSE and upper limb endpoints the multiple imputation approach will be used as described in the main analysis, based on the ITT Set. For the endpoints evaluating WHO motor milestones, the analysis will be performed as described but based on the IES. To further explore the response in the cohort of subjects in the IES for the HFMSE and upper limb endpoint the main analysis will be repeated. In these analyses if Month 15 is missing then the median of the MI values will be imputed. For HFMSE if the reason for the missing Month 15 value is treatment failure or death then they would be set to be a non-responder and this would override any imputation.

As an exploratory analysis for the WHO milestones the main analysis will be conducted based on data from Month 6, Month 9 and Month 12, separately. Specifically, let  $X$  denote Month 6, Month 9, or Month 12. The evaluable set at the interim analysis for the Day  $X$  visit is defined as the subset of subjects in the ITT Set who have the opportunity to be assessed at the Day  $X$  visit. Specifically, it will include all subjects with Day  $X$  visit and all subjects with time difference of at least  $X+7$  days between the date of first dose and the targeted clinical cut-off date of Aug 31, 2016 for the interim analysis. However, a subject who has died or withdrawn will be included provided that there is a time difference of at least  $X-7$  days between the date of first dose and the targeted clinical cut-off date of Aug 31, 2016 for the interim analysis.

In a situation where an interim analysis is performed and a subject is in the evaluable set for a summary of WHO milestones but has missing data at this visit then this will be imputed using the rules in Section 5.6.2 up to the last visit at which a subject qualifies for inclusion in an evaluable set. So a subject who is in the Month 12 evaluable set but not the IES and has a missing value at Month 12 then this will be imputed but a Month 15 value will not be imputed.

In the event of a successful interim and subjects rolling over early to open label treatment, for the early final analysis the secondary endpoints will be evaluated as described for interim and evaluable sets for Month 6, Month 9, and Month 12 visits will be similarly defined as subsets of the ITT Set.

### **5.6.8 Exploratory analysis**

For each secondary endpoint in order to further explore the change over time, the change from baseline to each visit or the proportion responding in each group at each visit will be analyzed as described in the main analysis for the final analysis. Summaries will be provided by treatment group.

The following displays may be presented by visit using observed data with no imputations for missing total scores:

- Thresholds of response in HFMSE, frequency and percentage
- Change in total motor milestones

- Change in upper limb score

Graphical representations to show each individuals response and Forest plots to summarize the primary endpoint and corresponding sensitivity analyses may also be presented.

Analyses will be conducted on the ITT Set and PPS.

## 5.7 Tertiary endpoints

### 5.7.1 Change from baseline in CSF SMN protein concentration

CSF SMN protein is collected pre-dose from subjects randomized to ISIS 396443 on Day 1 (the baseline assessment) and pre-dose on Days 29, 85 and 274.

The change and percentage change from baseline CSF will be presented by visit for subjects randomized to ISIS 396443. A plot of the mean and percentage change from baseline over time will be presented.

Scatter plots of change from baseline in HFMSE versus change from baseline in CSF SMN protein and corresponding Pearson's correlation coefficient will be presented by visit.

Analyses will be conducted on the ITT Set and PPS.

### 5.7.2 Clinical Global Impression of Change (Investigator and Caregiver assessments)

The Clinical Global Impression of Change (CGI) is assessed at five visits post first dose on Days 92, 169, 274, 365 and 456. At each visit the investigator and the subject's caregiver each score how the subject has changed compared to 'admission to the project'. The assessment is scored on a 7- point ordinal scale (1= Very much improved, 2 = "Much improved", 3 = "Minimally improved", 4= "No change", 5= "Minimally worse", 6= "Much worse", 7 = "Very much worse").

In order to investigate response on these scales, three definitions of responder will be defined: "Much improved": Responder ( $\leq 2$ ) versus Non-responder ( $\geq 3$ ), "Any improvement": Responder ( $\leq 3$ ) versus Non-responder ( $\geq 4$ ), "No worsening": Responder ( $\leq 4$ ) versus Non-responder ( $\geq 5$ ).

#### *Main analysis*

The proportion of subjects who were responders based on the "Much improved" definition of responder will be presented by visit.

#### *Exploratory analyses*

The main analysis will be repeated for the two alternative responder definitions of 'Any improvement' and 'No worsening'.

#### *Agreement between investigator and caregiver*

The agreement in assessment between the investigator and the caregiver will be examined. For each visit the proportion of assessments which agree (have the same assessed value) will be presented. In addition, at each visit the weighted Kappa coefficient will be calculated. No statistical significance testing will be performed but the coefficient will be interpreted in line with the ranges suggested by Landis and Koch (1977) for strength of agreement.

The analyses will be presented by treatment group and overall for the ITT Set.

#### *Exploring the relationship between CGI and HFMSE*

The change in HFMSE from baseline for CGI responders/non-responder defined using the 'Much improved' definition will be presented by treatment group, overall and by visit for both the investigator and caregiver assessment. A similar analysis will also be performed presenting the proportion of subjects who achieve at least 2, 3 and 4 points improvement in HFMSE for CGI responder/non-responder by treatment group, overall and by visit for the ITT Set.

#### **5.7.3 Change from baseline in Pediatric Quality of Life Inventory**

Subjects will be evaluated using the Pediatric Quality of Life Inventory (PedsQL™) Measurement 4.0 Generic Core Scales and 3.0 Neuromuscular Module (Varni et al. 1999) at screening (the baseline assessment) and on Days 92, 169, 274, 365 and 456.

The questionnaires are specific to the age of the subject, and sites are instructed to get both subjects and caregivers to complete the same age specific questionnaire as was collected at baseline irrespective of whether or not the subjects cross an age boundary at a subsequent visit.

The PedsQL parent questionnaire is collected for children in the following age categories: 2-4, 5-7, 8-12 and 13-18 years. Four dimensions are collected: Physical, Emotional, Social and School functioning and each item is scored on a 5 point ordinal scale (0= Never, 1 = Almost Never, 2= Sometimes, 3 = Often, 4 = Almost Always). The PedsQL patient questionnaire is collected for children in the following categories: 5-7, 8-12 and 13-18. Similar dimensions and 5-point ordinal scale are used as for the parents but for subjects aged 5 to 7 years a 3-point ordinal scale is collected, omitting the response levels of 1 and 3.

In the neuromuscular module, one parent questionnaire is collected for all subjects irrespective of age with three dimensions: 'About my child's neuromuscular disease', 'Communication' and 'Family resources'. The same 5-point ordinal scale is collected for each question. The patient neuromuscular disease questionnaire is collected for subjects in the following age categories: 5-7, 8-12, 13 -18. The questionnaire for subjects aged 5-7 years uses the 3-point ordinal scale as above and has only one dimension - 'About my Neuromuscular disease'. The questionnaires for the remaining two age categories cover dimensions for 'Communication' and 'Family resources' and use the 5-point ordinal scale.

In scoring a dimension the first step is to reverse and linearly transform to a 0-100 scale (0 = 100, 1 =75, 2=50, 3= 25, 4= 0), so a higher score is indicative of a better health related quality of life. If greater than 50 percent of the items within a dimension are missing then the dimension score will not be computed, otherwise the mean score for the dimension will be calculated as the sum of items over the number of items answered.

A psychosocial health summary score, constructed from three dimensions, will be calculated as the sum of items over the number of items answered in the emotional, social and school functioning scales. A total score will be calculated as the sum of all the items over the number of items answered on all the scales. If greater than 50 percent of the items are missing, then the summary score or total score will be set to be missing.

For the neuromuscular module, a score for each dimension and then total score will be calculated in the same manner, no health summary scores are evaluated.

For the generic PedsQL and neuromuscular module, the change and percentage change from baseline in the total score will be presented by visit and treatment group for both the parent and subject assessments. Similarly, the changes in the individual dimensions and health summary score will also be presented.

The change and percentage change from baseline score (each total score and parent/subject evaluation separately) to each visit will be analyzed using an ANCOVA model with treatment group as a factor and age at screening and baseline score as covariates. A statistical test for a treatment effect will be performed at Days 92, 169, 274, 365 and 456.

Multiple imputation as described in Section 5.3 will be used to impute missing post baseline values. The imputation will be performed separately for each dimension and total and psychosocial summary scores. Due to the age specific nature of these questionnaires, subjects aged 2-4 years would not be expected to complete the self-evaluation and if this is the case then imputations will not be performed and the subjects will be excluded from the analysis.

A plot of mean change from baseline (each questionnaire and parent/subject separately) based on the estimates from the ANCOVA model over time will be provided by treatment group.

Analyses will be conducted on the ITT Set and PPS.

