## 5. SUBJECT ELIGIBILITY

### 5.1 Inclusion Criteria

Subjects must meet all of the following criteria at Screening to be eligible:

1. Signed informed consent of parent or guardian. Signed informed assent of subject, if indicated per subject's age and institutional guidelines
2. Genetic documentation of 5q SMA (homozygous gene deletion, mutation, or compound heterozygote)
3. Onset of clinical signs and symptoms consistent with SMA at > 6 months of age
4. Males and females 2 to 12 years of age
5. Can sit independently, but has never had the ability to walk independently
6. Motor Function Score (Hammersmith Functional Motor Scale – Expanded)  $\geq 10$  and  $\leq 54$  at Screening
7. Able to complete all study procedures, measurements and visits and parent or guardian/subject has adequately supportive psychosocial circumstances, in the opinion of the Investigator
8. Estimated life expectancy > 2 years from screening, in the opinion of the Investigator
9. Meets age-appropriate institutional criteria for use of anesthesia/sedation, if use is planned for study procedures (as assessed by the Site Investigator and either anesthesiologist or pulmonologist)
10. For subjects who, in the opinion of the Investigator, have reached reproductive maturity, satisfy 1 of the following:

Females: have a negative pregnancy test at Screening and agrees to employ adequate contraceptive measures for the duration of the study. Acceptable contraception methods are restricted to abstinence, barrier contraceptives, intrauterine contraceptive devices or licensed hormonal products.

Males: be abstinent for the duration of the study

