#### *Multiple imputation for HFMSE , upper limb module test endpoint, PedsQL and ACEND*

Since month 15 HFMSE score values will not be available for many of the patients at the interim analysis, missing data will be handled using the multiple imputation (MI) method (Schafer 1997; Schafer 1999). The same method for imputation of missing values will be used at the final analysis.

The imputations will be performed on total scores for baseline and post-baseline visits. The Markov Chain Monte Carlo (MCMC) method will be used under the multivariate normality assumption to impute the missing score by treatment group. The treatment variable will be coded so that the ISIS 396443 group is the first in the sort order and therefore as the MI procedure is by treatment the imputation will be performed on ISIS 396443 subjects first.

Prior to the Proc MI step the dataset will be sorted by treatment and then ascending unique subject identifier (USUBJID). The variable list for imputations will include the baseline total score, age at consent, as well as all available post-baseline total scores. A set of 100 complete imputed data sets will be generated and the relative efficiency (RE) parameter will be checked. The RE is a very common parameter used in MI to determine the acceptability of the imputed results. Regarding the number of imputations, since the sample size in this study is relatively small and proportion of missing information is large, it will be important to run a large number of imputations to get an RE that is close to 98% or higher.

For PedsQL and ACEND the imputation will be performed independently on each dimension or summary score (constructed using all, or a subset of dimensions) separately, rather than at the item level.

The following pseudo SAS code and seeds will be used to perform the multiple imputation.

```
proc mi data =in_data    seed = x n impute = 100 out= imp_data;
  mcmc chain = multiple;
  var base age D92 D169 D274 D365 D456;
  by treatment;
  run;
```

---

Endpoint	Seed
HFMSE	25980495
Upper limb module test	47886416
PedsQL Core Parent	
Physical functioning	12676424
Emotional functioning	35764041
Social functioning	85032085
School functioning	79256650
Psychosocial health summary	74500750
Total Score	51407567
PedsQL Core Patient	
About my health and activities	48001267
About my feelings	21787096
How I get along with others	95088062
About School	11511569
Total Score	13067474
PedsQL Neuromuscular Parent	

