### *Multiple imputation analysis methods*

For the HFMSE, PedsQL, ACEND, upper limb module the imputations will be performed on the ITT population. In any sensitivity analyses using multiple imputation such as repeating the main analysis in the PPS the subset of subjects in the PPS will be selected from the multiple imputed datasets obtained from the ITT population. If the MI procedure imputes any

values outside the expected range for the scale e.g. from 0 to 66 for HFMS-E then values below 0 will be set to 0 and values above 66 will be set to be 66.

For each of the 100 imputed datasets, the endpoint will be compared between treatment groups using an ANCOVA model for continuous endpoints or logistic regression for binary endpoints as described in the main analysis for each endpoint. The estimates from the 100 fitted models will be combined to provide an overall estimate with corresponding confidence intervals and p-value [Little et al, 2002].

For the continuous endpoints, the difference between treatments and the corresponding CI will be presented. In addition, for each subject the median change from baseline to each visit will be calculated across the multiple datasets and summarized by treatment group. For the analyses using logistic regression the odds ratio and corresponding CI will be presented. In addition, the estimates of the binomial proportions in each treatment arm and the differences between treatments will be presented (Ratitch, 2013).

If, due to a small sample size or other unforeseen scenario, the multiple imputation model does not converge or encounters computational difficulties, then the number of iterations will be increased. If the model still fails then a Mixed Effects Model with Repeated Measures will be used as the primary analysis as described in Section 5.5.1.2.

In the presentation of results from multiply imputed data, the number of subjects with missing data and the degree to which it is missing will be summarized.

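### SAP 5.3 as written would impute two PedsQL neuromuscular self-report dimensions for children on the 5-7 form, who are never asked them, because the exclusion in SAP 5.7.3 covers only ages 2-4

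*SAP*

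**What the plan says.** Protocol 5.1 enrols "Males and females 2 to 12 years of age", so children aged 5-7 are in the ITT Set.

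SAP 5.7.3 describes the self-report instrument: "The patient neuromuscular disease questionnaire is collected for subjects in the following age categories: 5-7, 8-12, 13 -18". It then separates the forms: "The questionnaire for subjects aged 5-7 years uses the 3-point ordinal scale as above and has only one dimension", whereas "The questionnaires for the remaining two age categories cover dimensions for 'Communication' and 'Family resources". Sites are told to have subjects and caregivers "complete the same age specific questionnaire as was collected at baseline irrespective of whether or not the subjects cross an age boundary".

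SAP 5.3 sets the imputation rule: "The imputations will be performed on total scores for baseline and post-baseline visits". For PedsQL it applies this to each dimension or summary score on its own. The pseudo-code lists baseline, age and the five post-baseline visits as model variables and runs by treatment. The seed table has separate entries for Communication and for family resources under the patient neuromuscular heading. For PedsQL, among other scales, "the imputations will be performed on the ITT population".

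SAP 5.7.3 refers back to 5.3, but describes the values to be filled as missing values after baseline. Its one exception by age is for the youngest group: "subjects aged 2-4 years would not be expected to complete the self-evaluation and if this is the case then imputations will not be performed"; those children are also left out of the analysis. It attaches the ANCOVA and the tests at each visit to the total scores. For the individual dimensions it says only that changes will be presented.

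**The concern.** A score that is absent because the form does not contain the question is not a missing observation. Imputation cannot recover it, because there was never a value to recover. The plan recognises this for ages 2-4 and excludes them. The same section describes a second instance, the one-dimension form for ages 5-7, and no exclusion follows.

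If 5.3 is followed literally, the two dimension tables would be labelled ITT and would include children who never saw the questions. Their values would be extrapolated downward in age from children aged 8 and over, separately in each arm and from a small sham group. No child on the 5-7 form supplies any data against which that extrapolation could be checked.

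**Working it through.** The plan states no figure on this point, so there is none to reproduce. The check is mainly a reading of the text, followed by illustrative arithmetic.

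**1. Which children have the scores.** Communication and Family resources are on the 8-12 and 13-18 forms only. Enrolment stops at 12, so in practice they come from the 8-12 form. Because the baseline form is kept throughout, a child on the 5-7 form has neither score at baseline or at Days 92, 169, 274, 365 or 456: six cells per dimension, all empty by design.

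**2. What the imputation model does with such a child.** The model variables are the baseline score, age and five visit scores. Age is known for every child, so the record enters the model and a joint-normal procedure fills all six score cells. A toy run with this variable list (one arm, 64 children aged 5 or over, 23 of them aged 5-7 with every score missing) left 0 missing cells.

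**3. Whether the plan's own check would notice.** SAP 5.3 asks for a relative efficiency close to 98% or higher with m = 100 imputations. RE = 1/(1 + λ/m), where λ is the fraction of missing information.
- λ = 0.375: 1/(1 + 0.00375) = 99.6%
- λ = 1: 1/(1 + 0.01) = 99.0%

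Both pass, so this check cannot flag the problem.

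**4. How many children.** The documents give 126 enrolled (SAP 5.1) but no age distribution. Assuming an even spread over the 11 years of age from 2 to 12:
- aged 5-7: 126 × 3/11 ≈ 34
- aged 5-12, left after the 2-4 exclusion: 126 × 8/11 ≈ 92
- share of the latter on the 5-7 form: 3/8 = 37.5%

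If that share were 20% to 50% of 92, the number would be about 18 to 46.

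**5. Size if an ANCOVA were run on a dimension.** Assumptions, none from the documents: SD 20, visit correlation 0.6, no true effect, and the counts below. Each row used 150 simulated trials with 40 imputations (the SAP uses 100), drawn by arm given age and clipped to 0-100. Change at Day 456 was analysed by ANCOVA on treatment, age and baseline, and pooled by Rubin's rules.

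| Asked (active:sham) | Imputed (active:sham) | Share imputed | SE, asked only | SE, with imputed | Ratio |
|---|---|---|---|---|---|
| 24:12 | 14:7 | 21/57 = 37% | 5.7 | 8.8 | 1.5 |
| 20:10 | 20:10 | 30/60 = 50% | 6.4 | 11.5 | 1.8 |
| 16:9 | 24:12 | 36/61 = 59% | 6.8 | 14.1 | 2.1 |

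Repeat runs under the same assumptions gave 5.6-5.7 against 8.6-8.9, 6.2-6.3 against 11.6-11.8, and 6.6-6.7 against 14.4. The empirical spread of the estimate rose by less, 23% to 37% across runs, so the pooled standard error overstates the true variability. In keeping with that, the pooled test rejected in only 0 to 0.7% of null trials.

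**6. Effect on a descriptive table.** SAP 5.3 also summarises each subject's median change across the imputed data sets. Under the same assumptions, those medians had an SD of about 4 in the imputed active-arm children, against about 17 in observed children. If this summary is applied to the dimensions, the table would look more homogeneous than the data.

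**The case against.** The SAP nowhere says that it will impute scores for children on the 5-7 form. The section specific to PedsQL speaks only of values after baseline. On that reading a child with no baseline score has no computable change and drops out. The mechanism above needs the general sentence and the code in 5.3, which is labelled pseudo-code with an undefined input data set; a careful programmer could leave these children out. The reason given for the 2-4 exclusion, that the questionnaires are age-specific, already covers the principle. This stands in part: the two sections conflict, and the omission looks like a drafting slip. It does not dispose of the point, because 5.7.3 itself defers to 5.3, where text and code both include baseline, and nothing written excludes the 5-7 form.

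A second objection is that the standard errors describe an analysis that 5.7.3 does not name, since its ANCOVA and tests are for total scores. This stands. The general text in 5.3 speaks of an ANCOVA for each imputed continuous endpoint, but as described in that endpoint's main analysis, which leads back to the totals. The ratios therefore apply only if someone runs the model on these dimensions.

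Third, 5.3 requires the number of subjects with missing data and the extent of missingness to be summarised, so a reader would see how much was unobserved. This also stands. It discloses the count but does not stop the imputation.

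A reader might go further and infer that the sponsor chose to impute unasked questions, or that PedsQL tests could come out falsely positive. The documents support neither: the first is an unclosed gap, and for the second no test is named for these dimensions and the simulated error is on the conservative side.

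**Conclusion.** The point holds in a limited form. Following SAP 5.3 as written, and with only ages 2-4 excluded in 5.7.3, children on the 5-7 form would receive Communication and Family resources self-report scores generated entirely by extrapolation on age within arm. The wording of 5.7.3 on post-baseline values could be read to prevent this, and the two sections need reconciling.

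The consequence is small. It reaches the presented summaries of two self-report dimensions of one tertiary endpoint, for which SAP 5.2 makes no multiplicity adjustment. Primary, secondary and parent-reported results are not affected. The figures of about 34 children and of 1.5 to 2.1 times the standard error rest on an assumed age mix, SD and correlation. They illustrate scale and do not estimate what this trial would show. How the patient neuromuscular total is formed on the one-dimension form could usefully be footnoted, but that is clarification and not part of this finding.

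**What to change.** In SAP 5.7.3, after the sentence on ages 2-4, add: *For the patient neuromuscular Communication and Family resources dimensions, subjects on the 5-7 form are not imputed and are excluded from the analysis; the number administered the dimension is shown by arm.*

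Also make 5.3 and 5.7.3 agree on whether PedsQL baseline scores are imputed or only scores after baseline.

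The cost is one sentence, one filter in the program, and a smaller N in the two dimension tables. No other endpoint changes.
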